5.5 Rule of exclusion criteria of analysis sets

Table 1	Protocol deviations that cause natients to be excluded
	I TOTOCOL DEVIATIONS that cause patients to be excluded

Deviation ID	Description of Deviation (DVTERM)	Exclusion in Analyses	Severity code
INCL01	Informed consent missing or not signed prior to initiating study procedures.	EXCLUDE FROM FAS ITT SAF PP	6
INCL02	"Calculated Age" is expected to be equal or greater than 18 years or age is missing.	EXCLUDE FROM PP	4
INCL03A	Date of diagonosis of plaque type psoriasis is missing or difference between date of plaque type psoriasis and date of Visit date at Week 0 is less than 6 months	EXCLUDE FROM PP	4
INCL3B	Subject has psoriatic arthritis however does not satisfy classification criteria as per CASPAR.	EXCLUDE FROM PP	4
INCL04	Patient is a violator if:	EXCLUDE FROM PP	4
	- PASI less than 10		
	- PASI greater than 5 but less than 10 and DLQI less than 10		
INCL05	Patients candidate for systemic therapy, treatment naive or failed response to at least one systemic therapies	EXCLUDE FROM PP	4
EXCL02	Cyclosporine or methotrexate administration within 4 weeks prior to Day 1.	EXCLUDE FROM PP	4
EXCL03	Anti-TNF alpha therapy within timelines depending on drug half-life.	EXCLUDE FROM PP	4
EXCL04	Previous exposure to secukinumab or any other biologic drug targeting IL-17 or the IL-17 receptor	EXCLUDE FROM PP	4
EXCL05	Previous exposure to ustekinumab or any other biologic drug for the treatment of psoriasis that is not anti-TNF alpha therapy.	EXCLUDE FROM PP	4
EXCL06	Intravenous or intramuscular steroids within 2 weeks prior to screening and during screening.	EXCLUDE FROM PP	4
EXCL07	Ongoing use of corticosteroid topical treatments or UV therapy.	EXCLUDE FROM PP	4
EXCL15	Underlying condition that, in the opinion of Investigator, would pose a risk to subject safety or interfere with study evaluation, procedures and completion.	EXCLUDE FROM PP	4
EXCL16	Abnormal laboratory results at screening:	EXCLUDE FROM PP	4

Deviation ID	Description of Deviation (DVTERM)	Exclusion in Analyses	Severity code
	Liver tests: AST, ALT or ALP greater than $2.0 \times ULN$ or total bilirubin greater than $1.5 \times ULN$ (except for subjects with Gilbert Syndrome).		
EXCL19	Subject is currently enrolled in another investigational study.	EXCLUDE FROM PP	4
OTH08	PASI 50 not achieved at Week 16 however patient continued in the study.	EXCLUDE FROM PP	4
COMD01	Use of Prohibited medication (Ustekinumab as prior psoriasis therapy)	EXCLUDE FROM PP	4
COMD03	Use of Prohibited medication (Alefacept as prior psoriasis therapy)	EXCLUDE FROM PP	4
COMD05	Use of Prohibited medication (Etanercept as Prior Psoriasis Therapy)	EXCLUDE FROM PP	4
COMD07	Use of Prohibited medication (Adalimumab as Prior Psoriasis Therapy)	EXCLUDE FROM PP	4
COMD09	Use of Prohibited medication (Infliximab as Prior Psoriasis Therapy)	EXCLUDE FROM PP	4
COMD11	Use of Prohibited medication (Golimumab as Prior Psoriasis Therapy)	EXCLUDE FROM PP	4
COMD16	Use of Prohibited medication (Phototherapy as Prior Psoriasis Therapy)	EXCLUDE FROM PP	4
COMD18	Use of Prohibited medication (Other systemic psoriasis treatments)	EXCLUDE FROM PP	4
COMD19	Use of Prohibited medication (Topical treatment that is likely to impact signs and symptoms of psoriasis)	EXCLUDE FROM PP	4
COMD02	Use of Prohibited medication (Ustekinumab taken concomitantly)	EXCLUDE FROM PP	4
COMD04	Use of Prohibited medication (Alefacept taken concomitantly)	EXCLUDE FROM PP	4
COMD06	Use of Prohibited medication (Etanercept taken Concomitantly)	EXCLUDE FROM PP	4
COMD08	Use of Prohibited medication (Adalimumab taken concomitantly)	EXCLUDE FROM PP	4
COMD14	Use of Prohibited medication (Phototherapy taken concomitantly)	EXCLUDE FROM PP	4
COMD17	Use of Prohibited medication (Other systemic immunomodulating treatments)	EXCLUDE FROM PP	4
OTHER	No secukinumab administration	EXCLUDE FROM ITT SAF PP	2
OTHER	No valid PASI assessment after baseline	EXCLUDE FROM ITT PP	4

Deviation ID	Description of Deviation (DVTERM)	Exclusion in Analyses	Severity code
OTHER	Patient who didn't complete the study	EXCLUDE FROM PP	4
OTHER	Patient's without Cw6 assessment	EXCLUDE FROM ITT PP	5

Table 2Subject Classification rules

Analysis set	PD Population Codes that cause patient to be excluded	Non-PD criteria that cause a patient to be excluded
FAS	1,3	
ТТ	1,2, 4, 5	NA
Per-protocol	1,2,4, 5, 6	Not in ITT
Safety	1,2, 3, 6	No study drug taken

6 Reference

Expert panel on detection, evaluation, and treatment of high blood cholesterol in adults. Executive summary of the third report of the national cholesterol education program (NCEP) expert panel on detection, evaluation and treatment of high blood cholesterol in adults (Adult treatment Panel III). JAMA 2001; 285:2486-97.

Newcombe, R. G. "Interval estimation for the difference between independent proportions: comparison of eleven methods", Stat Med;17(8):857-72.

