7.2 Serious adverse event reporting

To ensure patient safety, every SAE, regardless of causality, occurring after the patient has provided informed consent and until 30 days after the last study visit must be reported to

Novartis within 24 hours of learning of its occurrence. Any SAEs experienced after the 30-day period should only be reported to Novartis if the investigator suspects a causal relationship to study treatment.

Recurrent episodes, complications, or progression of the initial SAE must be reported as follow-up to the original episode, regardless of when the event occurs. This report must be submitted within 24 hours of the investigator receiving the follow-up information. An SAE that is considered completely unrelated to a previously reported one should be reported separately as a new event.

The investigator will complete the SAE Report Form in English, assess the relationship to the study treatment and send the completed and signed form by fax within 24 hours to the local Novartis Drug Safety and Epidemiology Department Novartis (DS&E). The original and the duplicate copies of the SAE Form, and the fax confirmation sheet will be kept with the case report forms at the study site.

Follow-up information will be sent to the same person to whom the original SAE Form was sent, re-stating the date of the original report. A new SAE Form will be used (stating that this is a “follow-up”). The follow-up report should describe whether the event is resolved or continues, if and how it was treated, and whether the patient continued or discontinued study participation. The form and fax confirmation sheet will be retained at the study site.

If the SAE is not previously documented in the Investigator’s Brochure or Package Insert (new occurrence) and is thought to be related to the investigational treatment, a Drug Safety and Epidemiology Department associate may urgently require further information from the investigator for Health Authority reporting. Novartis may need to issue an Investigator Notification to inform all investigators involved in any study with the same investigational treatment that this SAE has been reported. Suspected Unexpected Serious Adverse Reactions (SUSARs) will be collected and reported to the competent authorities and relevant ethics committees in accordance with Directive 2001/20/EC or as per national regulatory requirements in participating countries.

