9.1 Analysis sets

The following analysis populations will be defined for statistical analysis.

- Full Analysis Set (FAS): all enrolled patients.
- Safety: all enrolled patients who were given at least one dose of study drug.
- Intent-to-treat (ITT): all patients included in the safety population with at least one post-baseline efficacy assessment.
- Per-Protocol (PP): all patients included in the ITT population who completed the study without any major protocol violation.

The primary and secondary objectives will be evaluated on the ITT population. A supportive analysis will be done on the PP population.

All safety evaluations will be based on the safety population.

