2.2 Analysis sets

The following analysis populations will be defined for statistical analysis.

- All patients: all patients who signed informed consent and entered in the study, including screen failure.
- Full Analysis Set (FAS): all enrolled patients (i.e. patients entered at week 0 visit 3).
- Safety: all enrolled patients included in the FAS population who were given at least one dose of study drug.
- Intent-to-treat (ITT): all patients included in the safety population with at least one post-baseline efficacy assessment and with the Cw6 assessment.
- Per-Protocol (PP): all patients included in the ITT population who completed the study without any major protocol violation.
- Core phase completers set: All patients who completed the Core phase visits (Week 24) are called core phase completer set.

The primary and secondary objectives will be evaluated on the ITT population. A supportive analysis will be done on the PP population.

All safety evaluations will be based on the safety set.

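### SAP 5.5 Tables 1 and 2 disagree on whether consent deviation INCL01 removes a patient from FAS and ITT, and INCL01 takes dosed patients who signed late out of Safety together with those who never consented

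*SAP*

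**What the plan says.** SAP 5.5 assigns patients to analysis sets through two tables. Table 1 lists deviations, each with a consequence and a severity code. INCL01 is "Informed consent missing or not signed prior to initiating study procedures", its consequence is "EXCLUDE FROM FAS ITT SAF PP", and its code is 6. Table 2 lists, for each set, the codes that exclude a patient:

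- FAS: 1, 3
- ITT: 1, 2, 4, 5 (non-deviation criterion: NA)
- Per-protocol: 1, 2, 4, 5, 6 (and not in ITT)
- Safety: 1, 2, 3, 6 (and no study drug taken)

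The sets are also defined in words. Protocol 9.1 defines Safety as "all enrolled patients who were given at least one dose of study drug". SAP 2.2 defines FAS as "all enrolled patients (i.e. patients entered at week 0 visit 3"), and Safety as "all enrolled patients included in the FAS population who were given at least one dose of study drug". In SAP 2.2, ITT is the part of Safety with a post-baseline efficacy assessment and a Cw6 result, and PP is a part of ITT. The primary analysis uses ITT and all safety evaluations use Safety.

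SAP section 4 lists the changes made to the analysis sets, among them the FAS condition for Safety and the Cw6 condition for ITT. It does not mention consent. Protocol 7.2 requires the reporting of "every SAE, regardless of causality, occurring after the patient has provided informed consent".

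**The concern.** There are two separate faults.

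First, Table 2 does not carry out Table 1. A programmer who works from the consequence column and one who works from the code lists will build different FAS and ITT sets, and ITT is the primary-analysis set.

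Second, INCL01 puts two different events under one rule. A patient who never consented is a clear case for exclusion. A patient who consented, but only after some procedure had begun, is not the same case. Protocol Table 6-1 places consent and the Cw6 and TNFα-308 determinations at Visit 1 (day -28), so a signature a day late could still come weeks before the first dose. Such a patient may be treated for up to 72 weeks and be absent from every adverse event, laboratory and exposure table. An SAE in that patient after signature would be reportable to the sponsor under protocol 7.2 and yet be missing from the safety tables.

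**Working it through.** **Set membership.** Take an enrolled, dosed patient who signed late and has a post-baseline PASI and a Cw6 result.

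| Set | Written definition (SAP 2.2) | Table 1 | Table 2, own row |
|---|---|---|---|
| FAS | in | out | in |
| Safety | in | out | out |
| ITT | in | out | not excluded |
| PP | out (SAP 2.3 lists INCL01 as a major deviation) | out | out |

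The tables disagree on FAS and ITT. They agree on Safety and PP. For Safety, both depart from the written definition.

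Table 2 is also inconsistent with SAP 2.2. By Table 2 the patient is in FAS and was dosed, so SAP 2.2 places the patient in Safety, but Table 2 says out. By Table 2 the patient is outside Safety but not removed from ITT, whereas SAP 2.2 makes ITT a part of Safety. The ITT row has no condition that refers back to Safety, while the per-protocol row does refer back to ITT. (The ITT row label is imperfect in the public text. The other three rows are FAS, Per-protocol and Safety, so it can only be ITT.)

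**The other codes used in Table 1.**

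- Code 2 (no drug given): Table 1 removes from ITT, Safety and PP. Table 2 agrees.
- Code 5 (no Cw6 result): Table 1 removes from ITT and PP. Table 2 agrees.
- Code 6 (INCL01): Table 2 omits FAS and ITT.
- Code 4: Table 1 removes from PP only in every row but one. The exception is no valid post-baseline PASI, which also leaves ITT. Table 2 lists code 4 in the ITT row, so read literally it removes all code 4 patients from ITT. Code 4 is therefore not usable as a PP-only code.

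**Size on the primary endpoint.** Inputs from protocol 9.7: 219 Cw6-positive, 146 Cw6-negative, 80% PASI 90 in Cw6-positive, margin 12 points. The protocol states 80% for Cw6-positive only; I assume the same in Cw6-negative. That assumption reproduces the planned power: SE = √(0.8 × 0.2 × (1/219 + 1/146)) = 0.0427; 0.12/0.0427 = 2.81; 2.81 − 1.96 = 0.85, which is about 80% power.

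Removing one patient from a cohort of n with rate p changes numerator and denominator together:

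- a responder removed: the rate falls by (1 − p)/(n − 1)
- a non-responder removed: the rate rises by p/(n − 1)

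| Cohort | Responder | Non-responder |
|---|---|---|
| Cw6-negative, n=146 | 0.2/145 = 0.14 points | 0.8/145 = 0.55 points |
| Cw6-positive, n=219 | 0.2/218 = 0.09 points | 0.8/218 = 0.37 points |

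Adding one patient gives nearly the same values.

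**Number of cases.** The documents give none. For illustration only, 0 to 2% of 406 enrolled patients would be 0 to 8.

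**The case against.** The strongest defence is that the text resolves most of this. Protocol inclusion criterion 1 and protocol 10.2 require consent before any study activity, so a sponsor may hold that an INCL01 patient was never properly enrolled. If Table 1 removes the patient from FAS, leaving Safety and ITT follows from the nesting in SAP 2.2. On that reading, the missing code 6 is a drafting slip in a lookup table.

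Part of this stands. Exclusion is defensible where consent was never obtained. It is also true that the Safety definitions require more than a dose: both require enrolment, and the SAP requires FAS membership. But SAP 2.2 spells out enrolment as entry at week 0, visit 3, with no condition on when consent was signed. Table 1's FAS exclusion therefore departs from the FAS wording itself, and section 4 does not declare it.

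Three stronger readings are tempting and are not supported.

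- A reader might infer that Safety membership depends on which table is used. It does not: both tables say out.
- A reader might take 1/146 = 0.68 or 1/219 = 0.46 points as the effect of one patient. Those are the effects of changing a patient's response, not of adding or removing the patient.
- A reader might infer that the patient vanishes from the report. SAP 2.3 gives reasons for exclusion from each set and summarises deviations on all patients, and SAEs after consent still reach the sponsor. What is lost is the patient's place in the safety tables.

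Protocol 8.1 requires monitors to verify fully that consent is present. That speaks to presence, not timing, but few or no cases is a realistic outcome.

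**Conclusion.** The point holds in two parts. Table 1 and Table 2 of SAP 5.5 conflict on FAS and ITT for code 6, and Table 2 alone yields a combination that SAP 2.2 rules out. Separately, a dosed patient who signed late is removed from all safety tables by a rule that the set definitions do not contain and section 4 does not declare.

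The effect on the primary result is small: at most about 0.55 points per patient against a 12-point margin, assuming 80% response in both cohorts and an unknown, possibly zero, number of cases. The documents do not support a claim that the primary conclusion is at risk. The reason to act is complete safety reporting, and analysis sets that come out the same whoever programs them.

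**What to change.** 1. Split INCL01 in Table 1. (a) Consent never obtained: exclude from all sets, keep code 6, and add code 6 to the FAS and ITT rows of Table 2. (b) Consent signed late: keep in FAS, Safety and ITT, exclude from PP only, and list as a deviation. Carry the split into the list of major deviations in SAP 2.3.
2. Give (b) a new code that appears only in the per-protocol row of Table 2. Do not use code 4, because the ITT row also excludes it. Reconcile code 4 at the same time: for example, give the no-valid-PASI row its own code for ITT and PP, and take code 4 out of the ITT row.
3. State how data collected before signature are handled, including baseline PASI. The documents leave this policy choice open. A rule that discards everything before signature would remove the baseline of anyone who signed after week 0, and with it the PASI 90 endpoint. The SAP already has a related rule in 2.1.1.5, where extension visit data are reported from the extension consent date on.
4. Declare in SAP section 4 whatever consent rule is adopted.

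The cost is one extra deviation row, two new codes, a few Table 2 entries and a short paragraph, all before database lock. The downside is that any late-consent patients stay in the main sets and must be shown as deviations.

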2.3 Patient disposition, demographics and other baseline characteristics

All data about patient demographics and baseline characteristics, including derived variables, will be summarized by cohort and overall with summary descriptive statistics on the Safety set. Continuous data will be summarized by n, mean, standard deviation, median, first and third quartiles, minimum and maximum. Categorical data will be presented by absolute and relative frequencies (n and %). P-values will also be displayed for both categorical and continuous variables, wherever required.

The number of patients in each analysis populations will be described and the reasons for excluding a patient from any particular population will be provided with the number of protocol violators for each criterion. The difference between cohorts with respect to protocol deviations and reasons for dropout will be examined by summarizing the protocol deviations by cohorts and overall on the all patients. Also, Major protocol deviations by cohorts and overall on the all patients.

Major protocol deviations are the deviations with Protocol Deviation IDs (DVSPID) as INCL01, INCL02, INCL03, INCL04, INCL05, EXCL02, EXCL03, EXCL04, EXCL05, EXCL06, EXCL07, EXCL15, EXCL16, EXCL19, COMD01, COMD02, COMD03, COMD04, COMD05, COMD06, COMD07, COMD08, COMD09, COMD11, COMD14, COMD16, COMD17, COMD18, COMD19, OTH08 and also patient's meeting the below criteria

• No secukinumab administration

- No valid PASI assessment after baseline
- Patient who didn't complete the study
- Patient's without Cw6 assessment.

Note:

- Prior use of prohibited PsO medication without the recommended wash-out period (PD: COMD01, COMD03, COMD05, COMD07, COMD09, COMD11, COMD16, COMD17, COMD18, COMD19).

- Concomitant use of PsO medication (PD: COMD02, COMD04, COMD06, COMD08, COMD10, COMD12, COMD14, COMD17, COMD18, COMD19).

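### SAP 5.5 Table 2 removes code-4 patients from the primary ITT set, although 31 of the 32 code-4 rows in Table 1 exclude from PP only and SAP 2.2 puts no completion or deviation test on ITT

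*SAP*

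**What the plan says.** SAP 2.2 defines ITT as "all patients included in the safety population with at least one post-baseline efficacy assessment and with the Cw6 assessment". SAP section 4 repeats this. Protocol 9.1 gives the same definition without the Cw6 condition. None of the three tests completion or protocol deviations. That test belongs to PP, which SAP 2.2 defines as "all patients included in the ITT population who completed the study without any major protocol violation". SAP 2.2 and 2.5.1 make ITT the primary set.

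SAP 5.5 then turns the sets into exclusion rules. Table 1 gives each deviation a text instruction naming the sets it excludes from, and a numeric severity code. Table 2 lists, for each set, the "PD Population Codes that cause patient to be excluded":

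| Set | Excluding codes in Table 2 |
|---|---|
| FAS | 1, 3 |
| ITT | 1, 2, 4, 5 |
| Per-protocol | 1, 2, 4, 5, 6 (and not in ITT) |
| Safety | 1, 2, 3, 6 |

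In Table 1, "Patient who didn't complete the study" and "PASI 50 not achieved at Week 16 however patient continued in the study" (OTH08) both carry code 4 and exclude from PP only. "No valid PASI assessment after baseline" also carries code 4 but excludes from ITT and PP. INCL01 (consent) carries code 6 with the instruction "EXCLUDE FROM FAS ITT SAF PP".

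**The concern.** The SAP holds two incompatible rules for the primary set and does not say which prevails. SAP 5.5 is a natural source for programming population flags, so the harm is real if Table 2 is the table that gets coded.

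In that case:

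- ITT loses every non-completer and every patient with a listed major deviation. SAP 2.3 opens its list with "Major protocol deviations are the deviations with Protocol Deviation IDs (DVSPID) as INCL01", and that list covers the same rows as Table 1. Table 2 therefore applies the PP test to ITT.
- The PP analysis stops being a separate check on the primary result.
- SAP 2.5.4 plans an ITT analysis that counts early discontinuers without a week-16 PASI as non-responders. No study discontinuers would be left to reclassify. The LOCF and NRI rules in SAP 2.5.3 would act only on completers with missed visits.
- OTH08 selects on outcome. A patient below PASI 50 at week 16 is necessarily a PASI 90 non-responder, and would be taken out of the primary analysis for that reason.

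The primary conclusion is a non-inferiority claim against a 12-point margin, so removing failures unevenly between cohorts can move it.

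**Working it through.** **1. Count of Table 1 (SAP 5.5).**

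| Code | Rows | Content |
|---|---|---|
| 2 | 1 | no secukinumab given |
| 4 | 32 | see below |
| 5 | 1 | no Cw6 assessment |
| 6 | 1 | INCL01 |
| Total | 35 | |

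Code-4 rows marked PP only: 5 INCL + 9 EXCL + 15 COMD + OTH08 + non-completion = 31. The remaining code-4 row is the one for no valid post-baseline PASI (ITT and PP). Cross-check: SAP 2.3 lists 30 deviation IDs plus 4 criteria = 34, and Table 1 splits INCL03 into two rows, giving 35.

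**2. Row-by-row match of Table 1 text with Table 2 codes.**

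| Set | Rows that disagree |
|---|---|
| FAS | 1 (INCL01) |
| ITT | 32 (31 code-4 rows, plus INCL01) |
| PP | 0 |
| Safety | 0 |

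Codes 1 and 3 in Table 2 have no row in Table 1.

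**3. ITT against PP under Table 2, with the nesting of SAP 2.2.** ITT lies within Safety, so its exclusions are {1,2,4,5} ∪ {1,2,3,6} = {1,…,6}. PP lies within ITT, so its exclusions are {1,2,4,5,6} ∪ {1,…,6} = {1,…,6}. The two sets are the same.

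**4. Check of the proposed fix.** Let the no-PASI row take a new code 7 and delete codes 1 and 3. Then FAS {6}, ITT {2,5,6,7}, PP {2,4,5,6,7}, Safety {2,6}. Disagreements over 35 rows and 4 sets: 0.

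**5. Planned sample size (not in dispute).** Inputs from SAP section 3: 80% in Cw6-POS, margin 0.12, one-sided 0.025, power 80%, ratio 219:146. An equal 80% in Cw6-NEG is assumed. n_POS = (1.960 + 0.842)² × 0.16 × (1 + 219/146) / 0.12² = 218.02, rounded up to 219. With 146 Cw6-NEG the total is 365, and 365/0.90 gives 406. Power at 219/146 is 80.2%.

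**6. Illustration only.** The documents give no share of patients with code-4 deviations, so every removal share below is assumed. Probability of passing = Φ((0.12 − d)/SE − 1.96), with unpooled SE, n_POS = 219(1 − f_POS) and n_NEG = 146(1 − f_NEG), where f is the share of the whole cohort removed.

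*False pass at assumed true rates of 80% POS and 68% NEG (nominal 2.5%).* Removal unrelated to outcome leaves it at 2.5%. If all removed patients are failures, the retained rates are 0.80/(1 − f_POS) and 0.68/(1 − f_NEG). Where the shares are of week-16 failures, f_POS is 0.20 times the share and f_NEG is 0.32 times it.

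| Removed POS/NEG | Shares of whole cohort: difference, false pass | Shares of week-16 failures: difference, false pass |
|---|---|---|
| 5%/10% | 84.2 − 75.6 = 8.7 points, 11.1% | 10.6 points, 4.9% |
| 5%/5% | 84.2 − 71.6 = 12.6 points, 1.8% | 11.7 points, 2.9% |
| 10%/5% | 88.9 − 71.6 = 17.3 points, 0.1% | 12.5 points, 1.9% |

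For 5%/5% even the direction depends on the base.

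*Power at 80% in both cohorts, from 219/146.* Removing 5% or 10% regardless of outcome gives 78.1% or 75.9%. Removing 5% or 10% who are all failures gives 85.1% or 92.4%. Power is unchanged when about 55% (5% removed) or 57% (10% removed) of the removed patients are responders.

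**The case against.** The strongest reply is that the intended ITT set is not in real doubt. SAP 2.2, SAP section 4, Protocol 9.1, the imputation rules in SAP 2.5.3, the ITT non-responder analysis in SAP 2.5.4 and the text column of Table 1 all keep deviators and non-completers in ITT. One cell of an appendix table says otherwise, and its probable cause is visible: one code-4 row does exclude from ITT, so a shared code cannot separate it from the rest. This is right about intent, and it is why the harm is stated as conditional. It does not make the cell correct. A final SAP should not leave a programmer to choose between two primary populations, one of which is the PP set.

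The power illustration can also be challenged on its base. The 365 already allows for 10% dropout, and with LOCF many dropouts stay in ITT. From 406 (60:40), power is about 84% before removal and about 80% after removing 10% regardless of outcome. That is a fair alternative. Code 4 also removes deviators and patients who leave after week 16, so starting from 219/146 is not an error.

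It is likewise true that the false-pass figures rest on assumed shares, and that patients and investigators are blinded to Cw6. Those figures are therefore no evidence of size or direction. Finally, Table 2 taken alone separates ITT from PP by code 6. The two sets coincide only once the nesting in SAP 2.2 is applied.

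**Conclusion.** The concern holds. Table 2 contains two coding errors: code 4 in the ITT row, which contradicts 31 rows of Table 1 as well as SAP 2.2, and code 6 missing from the FAS and ITT rows, which contradicts one row (INCL01). The second has limited effect on ITT, because ITT is nested in Safety and the Safety row already excludes code 6. The ITT row label is damaged in the text available here, but the other three rows are FAS, Per-protocol and Safety, so its identity is clear.

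The consequence depends on the sets being programmed from Table 2. If they are, the primary set becomes the PP set and the planned handling of discontinuers loses its subjects. The effect on bias or power cannot be sized or signed from the documents. Because a stated rule for the primary population is wrong as written and the correction is trivial, it should be made before the population flags are finalised.

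**What to change.** 1. Give the row for no valid post-baseline PASI its own code, list that code in the ITT and PP rows of Table 2, and remove code 4 from the ITT row.
2. Add code 6 to the FAS and ITT rows.
3. State that the definitions in SAP 2.2 govern wherever they differ from the tables in SAP 5.5, and define or delete codes 1 and 3.

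A separate minor correction concerns INCL04 in Table 1. Its first bullet flags every PASI below 10 as a violation, whereas inclusion criterion 4 in Protocol 4.1 admits PASI above 5 and below 10 when DLQI is at least 10. Reword it to match the protocol: violator if PASI ≤ 5, or if PASI is above 5 and below 10 with DLQI below 10. Once code 4 leaves the ITT row, this affects PP only.

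The cost is SAP table edits and the matching dataset flags. No new data, protocol change or added analysis is needed.
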